3.3 TERTIARY ANALYSES FOR THE VULNERABLE PATIENT STUDY

- To assess the risk of MACE based on the max 4 mm LCBI observed in any scanned portion of the coronary arteries excluding all sites in which PCI has been performed (either at the index event, or earlier)
- To assess NC MACE risk with area under the curve (AUC) analysis of a receiver operator characteristic (ROC) curve for varying threshold values of Max 4 mm LCBI.
- To investigate whether the risk of a coronary event increases with the number (count) of LRP's with max 4mm LCBI > 400.
- To characterize the extent (LCBI) and size (max 4mm LCBI) of LRPs among enrolled patients with ACS vs non-ACS, and with and without diabetes.
- To determine the relationship between the extent of LRP (LCBI of scanned artery) and size of LRP (max 4 mm LCBI) and the timing to the MACE.
- To compare the IVUS study variables (plaque burden, remodeling index, and MLA) in patients with MACE versus IVUS study variables in a randomly selected group of patients without MACE. For this group the study segments will be assessed for IVUS, NIRS and QCA findings.
- To compare the IVUS variables with the NIRS findings for patients with MACE versus a randomly selected group without MACE.
- To assess the primary endpoint (described above) with the addition of a NIRS thin-cap algorithm to identify LRPs with thick and thin caps (if available).

3.4 TERTIARY ANALYSES FOR THE VULNERABLE PLAQUE STUDY

- To assess the relationship between the size of LRP in a coronary artery segment (max LCBI > 4mm) and MACE with an AUC analysis of an ROC curve.
- To determine whether the incidence of NC-MACE attributable to a Follow up Culprit Lesion at a given site is dependent on the LCBI of the 30 mm segment, excluding sites (and their borders) in which PCI was performed prior to or at the time of index procedure.
- To assess the relationship between the maximum 4 mm LCBI detected in each 10mm segment of coronary artery scanned and the appearance of a new culprit lesion within the corresponding 10 mm segment of artery. These 10 mm segments will exclude sites (and their borders) that underwent PCI prior to or during the index event.
- The 10 mm segments will be given a hierarchal level with the higher assignment to those 10mm segments closer to the proximal portion of the scanned artery.

4 STUDY POPULATION

Screening will be performed in patients presenting for coronary angiography in whom IVUS and/or NIRS evaluation is planned or could be utilized as a part of their clinically-indicated evaluation. Written informed consent will be sought prior to the catheterization procedure for those meeting the general inclusion and exclusion criteria.

IVUS-NIRS imaging for a Suspected Index Culprit Lesion or Lesions and all clinically necessary treatment of Suspected Index Culprit Lesion(s) will be performed per standard practice. Patients who have provided written informed consent will then undergo IVUS-NIRS imaging of the Index Non-Culprit Arteries for research purposes during the catheterization. Those in whom the Investigator determines that acceptable IVUS-NIRS imaging has been completed in at least 2 major epicardial coronary arteries of at least 50mm of cumulative imaged artery will then be enrolled into the study. Patients will be considered screen failures if NIRS IVUS scanning is not performed in at least 2 epicardial coronary arteries or less than 50mm of cumulatively imaged artery.

Blinding

As noted above, IVUS-NIRS imaging of the culprit artery (before and if necessary after PCI) will be performed in an unblinded manner with full access by the clinical site to the results of IVUS-NIRS imaging. For NIRS imaging performed for research purposes in the Index Non-Culprit Arteries, the catheterization laboratory team will be blinded to the NIRS results. The team will not be blinded to the IVUS results in the Index Non-Culprit Arteries.

4.1 NUMBER OF SUBJECTS

The total study enrollment will be 9,000 patients.

Eligible subjects for this study will meet ALL of the following inclusion and NONE of the exclusion criteria.

4.1.1 INCLUSION CRITERIA

Subjects must meet all of the following inclusion criteria prior to enrollment in the study:

General Inclusion Criteria

1. Subjects presenting for coronary angiography in whom IVUS imaging is likely to be performed for clinical purposes.
2. Greater than 18 years of age.
3. Clinical presenting symptoms meeting one of the three criteria below:
 1. Subjects presenting with ACS defined as at least one of the following:
 - a) Elevated cardiac biomarkers with CK-MB or troponin greater than upper limits of normal range;
 - b) ST depression or ST elevation >1mm in 2 or more contiguous leads in the absence of LVH, paced rhythm, BBB or early repolarization;
 - c) A stabilized patient 24 to 72 hours post STEMI;
 2. Unstable angina pectoris;
 3. Stable Angina Pectoris and/or a positive functional study with evidence of ischemia.

Angiographic Inclusion Criteria

4. At least one Suspected Index Culprit Lesion requiring imaging with IVUS and/or NIRS for clinical indications.

5. At least two native epicardial coronary arteries (including the Suspected Index Culprit Artery) eligible for imaging with NIRS-IVUS

Total IVUS/NIRS Imaging Inclusion Criterion

6. A minimum of a total 50 mm of coronary artery not involved in a prior or Index Procedure PCI (including the 5mm borders on either edge of the site receiving PCI) must be scanned. This 50mm total length may include contributions from the Suspected Index Culprit Arteries and from Index Non-Culprit Arteries. This total length must include contributions from two or more native imaged arteries.

4.1.2 EXCLUSION CRITERIA

Subjects must meet none of the following exclusion criteria prior to enrollment:

General Exclusion Criteria

1. Unstable patients (STEMI within the prior 24 hours; cardiogenic shock, hypotension needing inotropes, hypoxia needing intubation, and IABP) and patients that had a procedural complication (coronary dissection, perforation or a complication that would necessitate immediate-unplanned revascularization) during index PCI procedure.
2. History of CABG or planned CABG within 6 months following NIRS-IVUS imaging.
3. Patient has additional lesion(s) that needs a staged PCI.
4. Subject life expectancy is less than 2 years at time of index catheterization.
5. Subject with ejection fraction (EF) <30%.
6. Subject pacemaker dependent/paced rhythm.
7. Subject pregnant and lactating.
8. Any other factor that the investigator feels would put the patient at increased risk or otherwise make the patient unsuitable for participation in the protocol.
9. Patients undergoing performance of PCI in all three major vessels during the index PCI.

4.2 REVIEW OF CHEMOGRAM TO DETERMINE PROTOCOL FOR FOLLOW-UP DEPENDING ON THE PRESENCE OR ABSENCE OF A LARGE LRP

At the end of the index procedure the chemogram (the NIRS findings output) data for both the Suspected Index Culprit Lesion or Lesions (unblinded) and Index Non-culprit (blinded) Arteries will be submitted to the NIRS Core Laboratory for evaluation. The Core Lab will review the chemogram to determine if a large LRP is present in an area that:

- 1) had not undergone PCI in the past,
- 2) did not undergo PCI at the time of the index procedure.

Areas that have undergone PCI (stent, balloon or other device) plus a 5 mm border on either side of the intervened area will be excluded from analysis.

A "large LRP" will be defined as a 4mm segment within the eligible area with an LCBI \geq 250.

The Large LRP Group: All patients with a large LRP will be followed with a phone inquiry at 2,6,12 and 24 months post enrollment.

The Small or No LRP Group: Of this group, 50% will be randomly assigned (in a 1:1 fashion) to be followed with a phone inquiry at 2,6,12 and 24 months post enrollment.

The follow-up status for each patient will be determined by the core lab and communicated to the site coordinator prior to the 2 month follow-up window for the call. The clinical site will remain blinded to the NIRS findings, as will the clinical events committee.

It is anticipated that approximately 1/3 of the 9,000 patients will have a large LRP, leading to complete follow-up in 3,000 patients with a large LRP and 3,000 with a small or no LRP.

5 STUDY DESIGN

This is a prospective, multicenter, international study that will enroll 9,000 patients presenting for a clinically indicated cardiac catheterization with IVUS-NIRS interrogation for a culprit or suspected-culprit lesion. Patients will be screened for enrollment into the study after they provide written informed consent and undergo IVUS-NIRS imaging of at least 2 coronary arteries, including the Index Culprit Artery. If PCI is performed during the index procedure, the artery length for study inclusion will exclude the segment undergoing PCI plus a border of 5mm on either side of the PCI treated segment. Patients in whom IVUS-NIRS imaging is performed in only one artery will be considered screen failures.

It is expected that IVUS-NIRS imaging of the Suspected Index Culprit Artery will be performed for routine clinical indications. For this reason both NIRS and IVUS data from the culprit artery will be available in an unblinded fashion to the clinical site.

[figure not shown]
IVUS imaging of Index Non-Culprit Arteries may be of immediate clinical value (detection of an unexpected stenotic area) while NIRS imaging of Index Non-Culprit Arteries will be performed for research purposes. Hence for the Index Non-Culprit Arteries, IVUS data will be available to the clinical site, but NIRS data will be blinded.

Follow-up will be conducted in 6,000 patients (as defined in figure 1) at 2,6,12 and 24 months to determine the occurrence of a NC-MACE and the relationship of a Follow up Culprit Lesion to the baseline characteristics of the coronary artery segment.

The expected 9,000 patients will be enrolled at up to 100 centers throughout the world. It is expected that enrollment for the LRP Study will start in January, 2014 and conclude in or around December, 2015. Therefore, follow-up for the last patient enrolled will conclude in December 2017.

If the goals of the study – identification of vulnerable patients and vulnerable plaque by IVUS-NIRS imaging – are achieved before the enrollment of 9,000 patients, the study will transition to a blinded, randomized study of the use of IVUS-NIRS imaging to guide treatment.

Figure 1: Proposed flow of patients in the Lipid-rich Plaque Study

*if available

5.1 STUDY ASSESSMENTS AND PROCEDURES

5.1.1 STUDY SCHEDULE

Table 1: Schedule of Contacts

	Index	60 days (± 14 days)	6 months (± 14 days)	12 months (± 14 days)	24 months (± 30 days)
Patient Data*	X				
Procedural details	X				
TVC Imaging	X				
Angiogram submission [§]	X	X [§]	X [§]	X [§]	X [§]
NIRS/IVUS submission [§]	X	X [§]	X [§]	X [§]	X [§]
Adverse Events	X				
MACE	X	X	X	X	X

*Demographics, medical history and risk factor review; [§]angiograms and NIRS IVUS data will be collected if MACE occur (no protocol driven follow up catheterization or protocol driven TVC will be performed). Patients with no large LRP who are not randomly assigned to the 2 year follow-up will still have their baseline data and procedural data recorded and submitted for analysis.

5.1.2 VISITS

5.1.2.1 INDEX VISIT

Screening:

As described above (Section 4) screening will be performed in patients presenting for coronary angiography in whom IVUS and/or NIRS evaluation is planned or could be utilized as a part of their clinically-indicated evaluation. Written informed consent will be sought prior to the catheterization procedure for those meeting the general inclusion and exclusion criteria.

IVUS-NIRS imaging for a Suspected Index Culprit Lesion or Lesions and all clinically necessary treatment of Suspected Index Culprit Lesion(s) will be performed per standard practice. Patients who have provided written informed consent will then undergo IVUS-NIRS imaging of the Index Non-Culprit Arteries for research purposes during the catheterization. Those in whom the Investigator determines that acceptable IVUS-NIRS imaging has been completed in at least 2 major epicardial coronary arteries of at least 50mm of cumulative imaged artery will then be enrolled into the study. Patients will be considered screen failures if NIRS IVUS scanning is not performed in at least 2 epicardial coronary arteries or less than a cumulative 50mm of artery is imaged.. No additional data will be collected on such patients.

Enrollment:

Patients with a successful IVUS-NIRS scan of >50 mm length in 2 or more arteries will be enrolled in the Study. IVUS-NIRS should be performed in 2 or more major epicardial arteries as mentioned above including the culprit artery.

The portion of the coronary artery or arteries to be studied will meet all of the following criteria:

- The portion of the coronary artery does not contain a flow-limiting stenosis, defined as > 50% diameter stenosis by visual angiographic estimate;
- The portion of the coronary artery has not undergone PCI in the past, and PCI is not performed at the index event or planned in a staged procedure. The length of artery excluded from the study because of PCI includes a 5mm border on either side of the intervened segment.

Suspected Index Culprit Lesion or Lesions -- IVUS-NIRS Assessment:

For a native artery deemed by the physician to require clinically-indicated IVUS interrogation, the TVC console will image and record the IVUS and NIRS findings in an unblinded fashion (meaning, both the IVUS and NIRS images and details as provided on the commercially available TVC system will be available to the clinical site for diagnosis and treatment of the artery). The TVC system will display the images and details for all pull-backs performed within the Suspected Index Culprit Artery throughout the imaging and, if needed, for treatment of the Index Culprit Artery. The denotation of "suspected culprit" and "culprit" will be recorded on the case report form.

Once the clinical team determines that all of the clinically-indicated IVUS has been completed, the clinical team will switch the TVC System to the NIRS-blinded mode, as specified in the Manual of Operations for the LRP Study.

Index Non-Culprit Artery or Arteries -- IVUS-NIRS Assessment:

For an artery that does not require clinically-indicated IVUS imaging, the TVC console will image and record the NIRS findings in a blinded fashion, only displaying the IVUS findings to the clinical site (meaning, only the IVUS images and details as provided on the commercially available TVC system will be available to the physician). The denotation of "non-culprit" will be recorded on the case report form.

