7 ADVERSE EVENTS

The IVUS-NIRS TVC catheter is designed to function as a conventional, rotating core, IVUS catheter which has an excellent safety record. Experience with NIRS in over 5,000 patients has shown that the TVC catheter safety profile does not differ from that of a conventional IVUS catheter. Therefore the potential adverse events associated with the IVUS/NIRS in the additional, non-culprit vessels are expected to be similar to those of the culprit and include, at a very low rate (<1%):

- Additional radiation exposure
- Heart arrhythmias
- Cardiac tamponade
- Injury to the arteries
- Low blood pressure
- Bleeding
- Stroke
- Heart attack
- Death

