7.2 REPORTING SERIOUS ADVERSE EVENTS

The Investigator shall report all Adverse Effects, whether device related or not, to the Sponsor and to the reviewing IRB as soon as possible (per the overseeing IRB's policy), but in no event later than 10 working days after the Investigator first learns of the effect. The Investigator must determine if the adverse event is "serious." The regulatory definition of "serious" is an event that is fatal or life threatening, resulting in a persistent or significant disability, requiring intervention to prevent permanent impairment/ damage, or an event that results in congenital anomaly, malignancy, hospital admission or prolonged hospitalization. Anything the investigator deems to be serious MUST be reported to the Sponsor within one business day from the knowledge and determination of the event.

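### The rule ending data collection on screen failures has no adverse-event exception and is not reconciled with the safety sections, so no denominator exists for complications of attempted research imaging

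*Combined protocol and SAP*

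**What the plan says.** Section 5.1.2.1 (Index Visit, Screening) sets the order of events:

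- Consent comes first: "Written informed consent will be sought prior to the catheterization procedure for those meeting the general inclusion and exclusion criteria".
- Research exposure follows: "Patients who have provided written informed consent will then undergo IVUS-NIRS imaging of the Index Non-Culprit Arteries for research purposes during the catheterization".
- Enrollment depends on the result. It is open to "Those in whom the Investigator determines that acceptable IVUS-NIRS imaging has been completed in at least 2 major epicardial coronary arteries", with at least 50 mm imaged in total.
- Otherwise: "Patients will be considered screen failures if NIRS IVUS scanning is not performed in at least 2 epicardial coronary arteries", or if the total length is under 50 mm.
- For these screen failures: "No additional data will be collected on such patients".

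Section 4 repeats the screen-failure rule without the last sentence.

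The safety provisions sit elsewhere. Table 1 (section 5.1.1) schedules adverse events at the index contact. Section 7.1 puts unanticipated adverse device effects on the subject's case report form. Section 7.2 states: "The Investigator shall report all Adverse Effects, whether device related or not", to the sponsor and the IRB within 10 working days, and anything judged serious to the sponsor within one business day. Section 12.2 requires notice to the IRB or ethics committee of such device effects and serious adverse events at the site, as local regulations require. Section 10.1 gives the safety committee the task of reviewing accumulating safety data, without defining the population.

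**The concern.** Imaging of non-culprit arteries is the procedure that the study adds for research. Angiography and PCI are done on clinical grounds, follow-up is by telephone, clinic contact or record review, and no catheterization is driven by the protocol afterwards. Sections 7 and 8.1 list arrhythmia, tamponade, arterial injury, stroke, heart attack and death among the possible adverse events of imaging the additional vessels.

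Each of these is a plausible reason to stop a pullback. If it stops before two arteries and 50 mm are reached, the patient is never enrolled. The enrolled cohort is then selected for having got through imaging, and selection depends on the very event that a safety summary should count. At stake is the committee's ability to judge the risk of the research procedure from a complete numerator and denominator.

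**Working it through.** **1. Setting the provisions side by side**

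| Provision | What it requires | Does it cover a consented screen failure? |
|---|---|---|
| 5.1.2.1 | No further data on screen failures | Yes, with no safety exception |
| Table 1 | Adverse events at the index contact | Not stated; screening belongs to that contact |
| 7.1 | Unanticipated device effects on the subject's form | Not stated whether a screen failure has a form |
| 7.2 | All adverse effects to sponsor and IRB | Not limited to enrolled patients |
| 12.2 | Device effects and serious events at the site to IRB/EC | Not limited to enrolled patients |
| 10.2 | Events committee reviews events in the follow-up period | No; screen failures never enter follow-up |

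No section says whether section 7 overrides 5.1.2.1. A coordinator who follows 5.1.2.1 to the letter and one who follows 7.2 would do different things for the same patient. The contrast with section 5.1.3 is also telling: enrolled patients allocated to no follow-up still have data collected through their hospital stay, while a patient exposed to the same catheter whose imaging was cut short does not.

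**2. Numerator and denominator**

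Section 7.2 can supply individual events. No section requires a count of consented patients in whom a research pullback was started, or the reason it ended early.

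**3. Direction of the bias**

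Let r be the true complication rate among patients in whom research imaging is started, q the share of those complications that lead to screen failure, and s the overall share of these patients who become screen failures. With 9,000 enrolled (section 4.1), the number imaged is M = 9,000/(1 − s). Then:

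rate among enrolled = M × r × (1 − q)/9,000 = r × (1 − q)/(1 − s)

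This is below r whenever q exceeds s, that is, whenever patients with a complication fail screening more often than patients overall. That is likely but not certain.

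**4. Illustration only**

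The documents give no value for r beyond an expectation of under 1%, and none for q or s. Assume r = 0.5% or 1%, q = 25%, 50% or 75%, and s = 2% to 10%. Example with s = 2%, r = 1%, q = 50%: M = 9,000/0.98 = 9,184; complications = 91.8; among enrolled = 45.9; rate = 45.9/9,000 = 0.51%.

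| r | q | s = 2%: complications in all imaged / in enrolled / enrolled rate | s = 10%: the same |
|---|---|---|---|
| 1% | 25% | 91.8 / 68.9 / 0.77% | 100 / 75.0 / 0.83% |
| 1% | 50% | 91.8 / 45.9 / 0.51% | 100 / 50.0 / 0.56% |
| 1% | 75% | 91.8 / 23.0 / 0.26% | 100 / 25.0 / 0.28% |
| 0.5% | 25% | 45.9 / 34.4 / 0.38% | 50 / 37.5 / 0.42% |
| 0.5% | 50% | 45.9 / 23.0 / 0.26% | 50 / 25.0 / 0.28% |
| 0.5% | 75% | 45.9 / 11.5 / 0.13% | 50 / 12.5 / 0.14% |

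The plan has no figure of its own to reproduce here: the expectation of under 1% comes without a derivation.

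**The case against.** The strongest reply is that safety reporting has its own route. Sections 7.2 and 12.2 are not limited to enrolled patients, and a rule against additional data does not erase what is already recorded. A pullback complication happens at the index contact, where Table 1 schedules adverse events. All of this stands. A reader might infer that these complications vanish from the safety record; the documents do not support that, since serious events should still reach the sponsor and IRB.

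Three further inferences also fail:

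- *That the safety committee is unable to compute a rate.* Section 10.1 lets it request any data it deems necessary and has it set its charter before the first data review. What is missing is a planned denominator.
- *That the protocol's under-1% statement is itself biased.* Sections 7 and 8.1 draw on earlier experience in over 5,000 patients. Nothing says this study will estimate or confirm that figure, and sections 3 and 6 plan no complication-rate estimate.
- *That the exclusion for procedural complications makes matters worse.* It concerns the index PCI. According to the synopsis, research imaging of non-culprit vessels begins after clinically indicated PCI, and the exclusion does not address it.

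The mechanism is also narrower than it may look. The suspected culprit artery counts towards both thresholds, so one adequate non-culprit pullback may suffice, and a complication after the thresholds are met does not cause screen failure. That lowers q by an unknown amount.

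None of this reconciles the provisions, and none of it supplies the count of attempted patients or the reason for stopping.

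**Conclusion.** The point holds as an unreconciled rule with a missing denominator. Section 5.1.2.1 ends data collection on consented patients who may already have been exposed to research imaging, without a safety exception, and conflicts with Table 1 and sections 7.1, 7.2 and 12.2. Any complication rate taken from enrolled patients would tend to be biased low.

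The direction rests on one assumption: complications end imaging short of the thresholds more often than patients in general fall short. The size cannot be estimated from the documents, and the figures in the table show only how the mechanism works.

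The primary hypotheses (H1 and H2) and their power calculations are unaffected, because they concern enrolled and followed patients. This is a cheap improvement to safety monitoring that should be made; it is no threat to the main analyses.

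**What to change.** Replace the no-data sentence in section 5.1.2.1 with a rule along these lines: for every consented patient in whom a research pullback is attempted, whether or not later enrolled, record the arteries attempted, the reason imaging stopped, and adverse events up to hospital discharge.

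Then:

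- state in section 7 that its reporting duties apply to these patients, and that they have a case report form for the purpose;
- define all consented patients with an attempted research pullback as the denominator for imaging complications, and tabulate complications over that group for the safety committee, with enrolled patients and screen failures shown separately;
- keep screen failures out of the analyses of H1 and H2.

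The cost is one short form for screen failures with an attempted pullback. No visits are added, since these patients have already consented and are in hospital.
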